- Lead impedance (atrial, ventricular, high voltage)
- Battery voltage
- Arrhythmia history
- Tachyarrhythmia therapy

The following pacemaker/ICD parameters will be deactivated for the duration of the MRI:

- Magnet response (ICD)
- Rate response
- PVC response
- Noise reversion response
- Ventricular sense response
- Mode switching
- Tachycardia detection/therapies (ICD)
- EGM triggers

Patients who are not pacemaker dependent will have their pacemaker/ICD programmed to AAI/VVI/DDI at 40 beats per minute for the duration of the MRI. Patients who are pacemaker dependent (pacing at programmed lower rate during the pre-scan interrogation) will have their pacemaker/ICD programmed to AOO/VOO/DOO at the programmed lower rate for the duration of the MRI. Emergency equipment, including a MRI compatible defibrillator and transcutaneous pacemaker, will be available throughout the procedure in the event of an adverse clinical event. In addition to radiology staff, a pacemaker technologist or manufacturer clinical representative and an EP tech/RN with current ACLS will be present for the duration of the procedure. An EP physician/advanced practice provider (APP) must be immediately available (i.e., in the hospital) to provide medical intervention, such as placement of a temporary external pacemaker if required. In the event that a code is called by the MRI staff, hospital protocol indicates that ER staff will respond to the code.

Radiology staff and the electrophysiology (EP) technologist or nurse with current ACLS certification will monitor the following patient parameters at least every 5 minutes throughout the MRI scan:

- Heart rate
- Heart rhythm
- Non-invasive blood pressure
- Oxygen saturation
- Symptoms

If any of the following adverse symptoms/events occur during the scan, the test will be immediately terminated:

- Burning/pulling sensation in device pocket/chest during MRI
- Potentially lethal/previously non-diagnosed arrhythmias during MRI
- Spontaneous and unanticipated pacing rate change
- SOB
- Chest pain
- Feeling of heat/pulling in the chest or device pocket

The patient will be removed from the scanner to the holding area and the device interrogated and reprogrammed to original parameters or as indicated by interrogation. If needed, emergency treatment will be provided as per ACLS protocols or at the discretion of the monitoring physician. The following parameters will be compared to the pre-MRI results:

- Patient's underlying rhythm

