- Atrial and right/left ventricular pacing thresholds
- P-wave and R-wave amplitude
- Lead impedance (atrial, ventricular, high voltage)
- Battery voltage

All device-related adverse events/symptoms will be documented on the data collection form and reported to the IRB. The patient will remain in the MRI suite holding area until medically stable. The need for further treatment will be at the discretion of the monitoring physician.

The EP physician/APP will review and compare the pre/post MRI device data prior to the patient's discharge from the MRI suite. Following testing, the pacemaker or ICD will be reprogrammed to the pre-procedure parameters. The need for device reprogramming related to the MRI scan will be based on the clinical judgment of the attending electrophysiologist.

Follow-up

Patients who do not experience a device-related adverse event will continue with their routine pacemaker/ICD follow-up.

Patients who experience one or more device-related adverse events during the MRI will return 1-7 days post-MRI for follow-up pacemaker/ICD testing to confirm appropriate function. At a minimum, device interrogation/testing will include:

- Atrial and right/left ventricular pacing thresholds
- P-wave and R-wave amplitude
- Lead impedance (atrial, ventricular, high voltage)
- Battery voltage

The need for further follow-up will be determined by the physician based on testing results and clinical need.

The results of the follow-up device interrogation, including whether MRI-related adverse events have resolved, will be documented and kept in the device chart and recorded in the Registry database.

If the insurance provider does not cover the MRI and device checks, those costs may be the full responsibility of the patient. The patient will be informed of the status of the pre-authorization before scheduling the MRI.

Inclusion Criteria

1. Patient has a non-MRI conditional permanently implanted pacemaker or ICD implanted after 2001
2. Patient has a strong clinical indication for MRI where MRI is the diagnostic modality of choice for specific disease state without acceptable alternative imaging technologies as determined by the ordering physician and a radiologist
3. Patient is at least 18 years of age
4. Patient is willing and able to sign study informed consent and HIPAA authorization

Exclusion Criteria

1. Non-device related contraindication for MRI (such as implanted metallic objects, claustrophobia, morbid obesity)

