2. Presence of capped/abandoned/epicardial leads or subcutaneous coil
3. Pregnancy
4. Device generator at elective replacement interval
5. Abdominal device implant

Adverse Events

For purposes of this registry, the following will be considered adverse events and will be reported to the IRB:

- Burning/pulling sensation in device pocket/chest during MRI
- Potentially lethal/previously non-diagnosed arrhythmias during MRI
- Spontaneous and unanticipated pacing rate change
- Power on reset
- Immediately post-MRI device parameter changes
 - Greater than 50 ohm change in atrial or ventricular (RV and/or LV) lead impedance
 - Greater than 5 ohm change in high voltage lead impedance
 - Greater than 50% decrease in atrial or ventricular (RV and/or LV) sensing threshold
 - Greater than or equal to a 1 volt increase in atrial or ventricular (RV and/or LV) pacing threshold
- MRI related device malfunction/failure
- Serious injury/death related to MRI device malfunction/failure

Changes in vital signs or termination of the scan not related to the presence of a pacemaker or ICD (i.e., anxiety-related increase in heart rate/blood pressure, tachypnea/SOB, etc) will not be considered adverse events and will not be reported.

All adverse events will be reported to the IRB in writing within 10 days of discovery. Any death of a patient will be reported to the IRB within 24 hours of discovery by research staff.

Sample Size

All patients who meet all the inclusion criteria and none of the exclusion criteria and who are willing sign the Registry consent/HIPAA Authorization will be enrolled in this registry at Lancaster General Hospital. Registry enrollment will continue indefinitely and/or until CMS approval of the procedure.

Any patient who signs the registry informed consent/HIPAA form but does not have an MRI will not be considered a registry participant (consented not enrolled). Patients who sign the research consent form and enter the MRI environment are considered enrolled, even if they do not successfully complete the scan.

Qualifications of Site Investigator:

Site investigators must be a board certified cardiac electrophysiologist or radiologist. The supervising physician/APP must be able to place and use a temporary external cardiac pacemaker. The facility must have the appropriate physicians and staff available for the insertion of an emergency temporary transvenous cardiac pacemaker if needed.

Data Collection

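### Does the adverse event list need a battery criterion because battery voltage is measured before and after the scan?

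*Combined protocol and SAP*

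**What the plan says.** In the combined protocol and SAP, Study Methods puts battery voltage on the pre-scan interrogation list. The post-scan list opens with "The following parameters will be compared to the pre-MRI results" and ends with "Battery voltage". The same section adds, for the time before the patient leaves the MRI suite, "The EP physician/APP will review and compare the pre/post MRI device data". The Follow-up section lists battery voltage again among the minimum tests at the return visit, which it introduces with "Patients who experience one or more device-related adverse events during the MRI will return 1-7 days post-MRI".

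Exclusion Criteria, item 4, bars a patient with "Device generator at elective replacement interval".

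The Adverse Events section has seven top-level items. One of them, "Immediately post-MRI device parameter changes", is a heading over four numeric cut-offs. Two others matter here: "Power on reset" and "MRI related device malfunction/failure". Data Collection then says that incidence will be tracked for adverse events as the protocol defines them. Study Results makes that incidence a minimum item in the reports to the IRB and CMS.

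**The concern.** The protocol treats battery status as important enough to keep a patient out and measures voltage at each interrogation, but gives no rule for counting a battery change as an outcome. The other numeric device measures have a cut-off that applies on the reading alone, and nobody has to attribute the change to the scan. An isolated battery finding has to pass through "MRI related device malfunction/failure", which is undefined and needs a judgement of both cause and malfunction. Two patients with the same post-scan finding could then be classified differently, and the incidence reported to the IRB and CMS would depend on who reviewed the case. Enrolment is open-ended, so different reviewers could apply different habits over time.

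A side point is that Follow-up speaks of events during the scan, while the parameter changes are immediate post-scan findings. It could seem unclear whether a parameter change of any kind leads to the return visit.

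**Working it through.** The plan states no sample size, event rate, voltage standard deviation or test for this point, so there is no figure to reproduce. The check compares what is measured with what is counted.

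**Adverse event criteria.** Seven top-level items, one of which is a heading over four cut-offs: 7 − 1 + 4 = 10 criteria. Number naming battery voltage or elective replacement: 0 of 10.

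**Measurements against cut-offs.**

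| Numeric measure compared after the scan | Cut-off in Adverse Events |
|---|---|
| Pacing threshold | increase of at least 1 V |
| P-wave and R-wave amplitude (read as sensing) | decrease of more than 50% |
| Pacing-lead impedance | change of more than 50 ohm |
| High-voltage lead impedance | change of more than 5 ohm |
| Battery voltage | none |

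So 1 of 5 measures has no cut-off, or 1 of 4 if impedance is counted once. Underlying rhythm is also compared after the scan and has no parameter-change cut-off either. The plan therefore does not follow a rule that every compared item must carry one.

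**What is collected.** Battery voltage is on 3 of 3 interrogation lists, with two qualifications.
- The post-scan list directly follows the text on terminated scans. Applying it to completed scans is an inference. It is supported by the review of device data before discharge (Study Methods) and the review of each patient's pre- and post-procedure data (Data Collection).
- All three lists name voltage. Elective replacement status appears only as an exclusion. The measurement already in hand is voltage, and a criterion based on post-scan replacement status might need a data field that the documents do not show.

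**Who sees a battery change.** There are four routes: the pre-discharge review by the EP physician or advanced practice provider (Study Methods); a study electrophysiologist's review of each patient, and the at-least-quarterly analysis, which looks at which devices are affected and how (both Data Collection); and the Safety Committee's review every 6 months (Data Monitoring Safety Plan). Study Results also requires patient outcomes in the IRB and CMS reports.

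**Size.** If k isolated battery findings occur among n scanned patients and are left out, patient-level incidence falls by k/n. At the review set for the first 25 patients, one such finding would move it by 1/25 = 4 percentage points. The documents give no value for k. Neither the hazards listed in Background nor those under Risks of Study Participation include battery depletion. The second list does include the possible need for a new device, without tying it to the battery.

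**Recoverability.** Where paired voltages exist, any counting rule can be applied later to all patients alike. No patient would need to be measured again.

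**The case for a change.** The strongest case for a change is that a written rule is cheap and removes discretion from a reported rate. One line in the event list, or one sentence saying that voltage change is descriptive, would do it. "Power on reset" helps only when it happens alongside the battery finding. Reading the parameter-change heading as open-ended would still leave no battery criterion. All of that stands as a description of the text.

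It does not show that following the plan gives a wrong answer. Inconsistent counting is possible but not demonstrated. Choosing which device measures carry a cut-off is an electrophysiology judgement, and the protocol may reasonably leave voltage as a reviewed measurement. Adding a criterion is not purely a counting matter either, since Follow-up links device-related adverse events to a return visit.

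The timing point has some substance as loose wording, but it is separate from the battery. The preceding sentence in Follow-up sends to routine care only patients without a device-related adverse event and sets no limit on timing. The return visit also retests the measures that carry cut-offs. Both favour a reading that includes post-scan parameter changes. If the sponsor wants the two sections to match exactly, it can reconcile them; no clinical rule is suggested here.

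**Conclusion.** No change follows. The gap in the text is real: 0 of 10 criteria mention the battery, and battery voltage is the one numeric measure of five without a cut-off. It is a gap in classification and not in detection, and the people who run the registry can fill it sensibly. The reviewing electrophysiologist can use "MRI related device malfunction/failure" where a battery finding warrants it, and the analyst can summarise paired voltages descriptively.

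The effect on incidence cannot be sized from the documents. It would be one patient in the denominator for each isolated finding, and nothing in the documents gives reason to expect many. The conclusion assumes that post-scan voltage is recorded for completed as well as terminated scans, and that the per-patient electrophysiology review takes place as described in Data Collection. If post-scan voltage were not recorded for completed scans, the problem would be missing data, and a battery criterion would not cure it.

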In recent years, however, several studies have concluded that MRI can be safe for patients with non-MRI conditional pacemakers and/or ICDs (Nazarian, et al, 2006, 2011). In these studies, investigators limited the MRI scans to magnets generating a field of 1.5 Tesla. Initially, the specific absorption rate (SAR) was limited to ≤ 2.0 W/kg, but as investigators found no association between SAR and the device variables studied, that restriction was later removed (Nazaraian, 2011). In 2011 Nazarian, et al published the results of their study of patients with pacemakers (237) or ICDs (201) who underwent medically indicated MRI. The study indicated that MRI is safe for pacemaker and ICD patients when appropriate screening protocols are in place and followed, with no immediate or long-term events requiring lead or system revision or reprogramming (Nazarian, et al., 2011). A 2008 study determined that MRI scanning did not cause sufficient damage to the myocardium to produce a significant rise in troponin-I levels (Mollerus, Albin, Lipinski, & Lucca, 2008). In 2009, Mollerus et al also determined that device patients undergoing MRI did not have any increase in arrhythmic activity during the scan (Molerus, Albin, Lipinski, & Lucca, 2009).

Registry Purpose

This registry is a prospective single institution study of MRI examinations in patients with pacemakers or ICD's who will undergo an MRI that is ordered for routine clinical care. The purpose of the registry is to

accumulate pre-and post-scan device interrogation data for the purpose of determining the risk of MRI for patients with implantable devices.

Registry data will add to existing data on the safety of MRI scans for patients with pacemakers and ICDs. This safety data may impact physicians' diagnostic choices for this patient population. Patients with conditions for whom MRI is the best diagnostic modality but who have not been able to undergo MRI scanning may be able to do so through registry participation. The diagnostic information obtained from the scan may assist physicians' treatment decisions and may ultimately affect patient outcomes.

In addition, to our knowledge, previous registries of MRI's in non-conditional cardiac devices have been limited to academic centers. This registry would be among the first to demonstrate the feasibility and safety of this approach in a community hospital setting.

Study Methods

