The registry research involves acquiring and analyzing the data of device function and adverse events related to the MRI scan.

The need for MRI will be determined on a case-by-case basis based on the patient's medical history and treatment plan/goals, independent of the registry and research purposes. Only patients with implanted devices with orders for clinically indicated MRI scans will be considered for registry inclusion. Clinical review will be performed and the patient considered after determination that no other imaging modality would be appropriate.

The appropriateness of the MRI study must be discussed, in person or via phone call, between a cardiac radiologist, as determined by [name]., and the requesting physician. The discussion should include consideration of alternative imaging modalities and diagnostic quality of MRI imaging of requested body region given implanted device(s). The requesting physician is then responsible for discussing with the patient and/or their medical proxy the reasoning for the determination, based on the final decision made by a radiologist.

All patients will be screened prior to enrollment. Any patient with any commercially available pacemaker or ICD system implanted after 2001 who meet all of the inclusion criteria and none of the exclusion criteria, and who require a medically-indicated MRI as described above will be eligible to enroll in the study. The presence/absence of capped/abandoned/epicardial leads/subcutaneous coil will be confirmed and documented by review of the most recent chest x-ray obtained. The x-ray must post-date the most recent device/lead intervention, as determined by a review of the patient's medical record.

If an MRI procedure is deemed absolutely necessary, the MRI will be performed at the Lancaster General Hospital Lime Street MRI facility. MRI scan sequences, field intensity and field(s) of exposure will be selected to minimize risk to the patient while gaining needed diagnostic information for diagnosis or therapy management.

The MRI will be performed with a 1.5 T scanner utilizing institutional protocols and the following settings:

- Normal operating mode
- SAR \leq 2.0 W/kg per patient.

Prior to the procedure, a pacemaker technologist or manufacturer clinical representative will interrogate the pacemaker or ICD and record the following parameters:

- Patient's underlying rhythm
- Atrial and right/left ventricular pacing thresholds
- P-wave and R-wave amplitude

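### Shortness of breath and chest pain stop the scan but are not on the adverse-event list, and no count of terminated scans is required, so a device-related symptom stop may be left out of the reported incidence

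*Combined protocol and SAP*

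**What the plan says.** All references are to the combined protocol and SAP.

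- **Registry Purpose and Study Methods.** The aim is "determining the risk of MRI for patients with implantable devices", and the research consists of "acquiring and analyzing the data of device function and adverse events related to the MRI scan".
- **Study Methods, stop list.** "If any of the following adverse symptoms/events occur during the scan, the test will be immediately terminated". Six items follow. They include shortness of breath, chest pain and "Feeling of heat/pulling in the chest or device pocket".
- **Study Methods, after a stop.** "All device-related adverse events/symptoms will be documented on the data collection form and reported to the IRB".
- **Follow-up.** "Patients who experience one or more device-related adverse events during the MRI will return 1-7 days post-MRI" for device testing.
- **Adverse Events, definition.** "For purposes of this registry, the following will be considered adverse events and will be reported to the IRB", followed by the list. A closing sentence deals with vital-sign changes and terminated scans that are unrelated to the device, with anxiety effects as the example: "tachypnea/SOB, etc) will not be considered adverse events and will not be reported". The condition that they be unrelated to the device comes earlier in that sentence and governs it.
- **Data Collection and Study Results.** The incidence tracked is that of adverse events as the protocol defines them. The minimum report refers back to the same description.
- **Sample Size.** A patient who has consented and enters the MRI environment is enrolled, even if the scan is not completed.

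**The concern.** The stop list and the adverse-event list serve the same registry and overlap, but they do not match. Study Methods treats all six stop triggers as adverse symptoms or events. The Adverse Events section, which is the only explicit definition, does not carry all six over. If incidence is counted from that definition, a scan stopped for device-related chest pain or shortness of breath need not count, although it was serious enough to end the examination.

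Attribution adds to the problem. Shortness of breath is a stop trigger in one section and an example of an unrelated, unreported change in another. No criteria say how to tell the two apart. A reader of the results could not see how many scans were stopped for symptoms or how the stops were attributed.

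Results go to the IRB, to CMS and to journals, and the protocol says the data may widen routine use of MRI in these patients. An adverse-event rate that two careful people could count differently is a weak basis for that.

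**Working it through.** The documents state no event rate, sample size or precision target, so there is no figure to reproduce. The check sets the lists side by side.

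**Step 1. Stop triggers (Study Methods) against the adverse-event list (Adverse Events).**

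| Stop trigger | On the adverse-event list? |
|---|---|
| Burning or pulling in pocket or chest | Yes, same wording |
| Dangerous or newly seen arrhythmia | Yes, same wording |
| Unexpected pacing rate change | Yes, same wording |
| Heat or pulling in chest or pocket | In part: pulling is named, heat only by way of burning |
| Shortness of breath | No |
| Chest pain | No |

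Totals: 3 in full + 1 in part + 2 absent = 6.

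**Step 2. Lines on the adverse-event list.** There are seven bullets. One is a heading over four device-parameter changes, so the event lines number 6 + 4 = 10. Lines naming shortness of breath or chest pain: 0 of 10. In that section shortness of breath appears only in the closing exclusion sentence.

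**Step 3. Minimum report (Study Results).** The items are patients screened, patients scanned, device models, adverse-event incidence and description, and patient outcomes: five. Items that count terminated scans: 0 of 5. Patient outcomes are not defined and the list is a minimum, so terminations could be reported, but nothing in the visible text requires it.

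**Step 4. Path of one case.** Take a scan stopped for chest pain judged device-related, with no listed arrhythmia, rate change, reset, parameter change or malfunction.

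- Under Study Methods it is documented and sent to the IRB.
- Under Adverse Events it matches none of the 10 lines.
- Under Data Collection, incidence follows the protocol's definition, so on the list as written the case is not counted.
- Under Study Results, the reference back to the description above could be read to take in the Study Methods sentence, in which case it is counted.

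The text supports both answers.

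**Step 5. Denominator.** Sample Size counts incomplete scans as enrolled. Study Results asks for numbers screened and scanned. No section says which is the denominator of the incidence.

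**Step 6. Illustration only.** Data Collection sets a review after the first 25 patients scanned. Suppose there is no other adverse event and *x* device-related symptom stops are uncounted; *x* is an assumption. The rate is *x*/25 with the exact (Clopper-Pearson) 95% interval, whose upper limit is the 0.975 quantile of Beta(*x*+1, 25−*x*).

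- *x* = 0: 0/25 = 0%; upper limit 1 − 0.025^(1/25) = 13.7%.
- *x* = 1: 1/25 = 4%; interval 0.1% to 20.4%.

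This shows how much one case can matter at that review. It does not estimate how many cases there will be.

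**The case against.** The best reply has four parts.

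1. **The exclusion is qualified.** It removes only changes and terminations unrelated to the device and does not exclude device-related shortness of breath. This is correct. The gap is that device-related shortness of breath and chest pain have no line of their own on the list.
2. **The list may be open.** The text does not say that only the listed items count. If it were closed, a sentence excluding unrelated terminations would hardly be needed. Study Methods also treats device-related events and symptoms as one category that goes to the IRB. This is a fair reading, but not the only one, and the protocol does not choose between them.
3. **The uncounted case is narrow.** After a stop the device is interrogated and compared with its pre-scan values, so many device effects would surface as a listed event. An investigator electrophysiologist reviews each patient's device data, vital signs and adverse events, and the Safety Committee reviews the study data. This limits the likely number of missed cases and means the source records are not lost. It supplies no relatedness criteria and does not make the reported results show the stops.
4. **Heat is nearly covered.** The heat trigger and the burning line share location and the word pulling, so heat is the weakest of the three. General warmth is also listed as an ordinary MRI effect under Risks of Study Participation. The same section names device heating with discomfort or tissue damage as a device risk, so a plain mention of heat is still worth having.

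Leaving out stops that are correctly judged unrelated causes no bias. The case for tabulating them is that readers can then see how the judgement was made.

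**Conclusion.** The concern holds. Two of the six stop triggers are absent from the adverse-event definition and a third is covered only in part. The minimum report does not require a count of terminated scans, the rule for relatedness is missing, and the incidence denominator is not stated. As written, a device-related symptom stop can be counted or left out.

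Any bias in the reported incidence is downward. Its size is unknown and may be zero, because the documents give no rate of such stops. Confidence is high in the mismatches; it does not extend to the size of any understatement. The data collection form is not in the documents and the study algorithm in Appendix A is not shown, so the conclusion is limited to the visible text. This is a cheap improvement to reporting, not a flaw that undermines the registry.

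**What to change.** 1. Reconcile the stop list, the device-related symptom sentence in Study Methods and the Adverse Events list, so that device-related shortness of breath, chest pain and heat in the chest or device pocket count in the adverse-event incidence.
2. Replace the non-reporting rule for terminations with text such as: *Every terminated scan is recorded with its reason and attribution (device-related, not device-related, undetermined). The number of terminated scans by reason and attribution is reported beside the adverse-event incidence, with all enrolled patients as the denominator.*
3. Add one sentence on who makes the attribution and on what basis.

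Stops judged unrelated appear in this table only. They do not become adverse events and do not trigger the 10-day IRB report. A sensitivity count that adds undetermined symptom stops is optional. The clinical stopping rule is not touched. The sponsor should state whether newly counted events fall under the 1–7 day return visit.

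The cost is a few lines of protocol text, one data field if the form lacks it, and one row in each report. IRB reporting grows little, because device-related symptoms already go there. If the sponsor applies the return visit to these events, those patients have an extra device check, and the protocol says uncovered checks may be at the patient's expense. The reported rate may look slightly less favourable.
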